Subjects will first be randomized in a 1:1 ratio to either PROKERA® Arm (i.e., PROKERA plus SOC) or Control Arm (i.e., SOC only) by a computer-generated randomization code. For the PROKERA® Arm, one eye of each subject will be randomly assigned as the primary study eye.

CLINICAL STUDY PROTOCOL
STUDY FLOWCHART:

STUDY PRODUCT AND MODE OF ADMINISTRATION:

PROKERA® is manufactured by TissueTech, Inc. (Miami, FL), and is distributed by BioTissue, Inc., which is a solely owned subsidiary of TissueTech, Inc. PROKERA® is a corneal-epithelial insert, consisting of an ophthalmic conformer that incorporates cryopreserved amniotic membrane. PROKERA® is a Class II medical device that was cleared by the FDA under 510(k) #K032104 with the intended use in eyes in which the ocular surface cells have been damaged, or underlying stroma is inflamed and scarred.

Following the evaluations performed at the baseline visit, PROKERA®(Slim) will be inserted in the subject's primary study eye between the ocular surface and the eyelid as follows:

1. Apply topical anesthesia
2. Hold the upper eyelid

CLINICAL STUDY PROTOCOL

3. Ask the subject to look down
4. Insert the PROKERA® into the superior fornix
5. Pull lower eyelid down and slide PROKERA® under the lower eyelid
6. Check centration under the slit lamp
7. Apply a tape-tarsorrhaphy over the lid crease (standardized/specified in the full study protocol).

STUDY POPULATION/ DURATION:

A minimum of 50 subjects with moderate DED will be enrolled and randomized in this study. Following the baseline visit at which the subject will be randomized to either PROKERA® Arm or the Control Arm, one of the two eyes will be designated as the primary study eye. Each subject will be evaluated for a period of three months.

PARTICIPANTS' ELIGIBILITY:
Inclusion Criteria

- Subjects with moderate dry eye defined as corneal fluorescein staining score of ≥ 3
- Age ≥ 18 years
- Distance best corrected visual acuity better than 20/60 Snellen equivalent in each eye
- Willing to sign a written informed consent to participate
- Able to follow study instructions, with the intention of completing all required visits

Exclusion Criteria

- Presence of persistent corneal epithelial defect or ulcer in either eye
- Presence of active ocular infection in either eye
- Presence of ocular inflammation that is not related to keratoconjunctivitis sicca, e.g., allergy, severe blepharitis

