The sample size is estimated according to the outcomes reported by John et al.¹¹ The mean corneal fluorescein staining score does not change in the control group (2.8 at baseline and 2.9 at 3 months) while PROKERA® group reduces the corneal staining from the mean grading score of 2.8 at baseline to 0.8 (SD=0.4) at 1 month and 0.6 (SD=0.5) at 3 months in patients with moderate to severe DED. This result yields a reduction of more than 70% or an effect size of more than 2.0 over 3 months from baseline.

Assuming a large effect size of at least 0.85 for the PROKERA® Arm (i.e., PROKERA® plus SOC) against the Control Arm (i.e., SOC only) at 1 month from baseline for the corneal fluorescein staining score, 23 subjects per group or 46 subjects in total are needed to be randomized to yield an 90% power at a 2-tailed significance level of 0.05, using two-sample t-test, to detect such a difference between the two treatments. The effect size of 1.00 is equivalent to a reduction of approximately 35% in corneal fluorescein staining score from baseline for the PROKERA® Arm compared to the Control Arm. To further account for an around 10% dropout, the study plans to enroll and randomize 50 subjects in total.

CLINICAL STUDY PROTOCOL
REFERENCES

1. The definition and classification of dry eye disease: report of the Definition and Classification Subcommittee of the International Dry Eye WorkShop (2007). *Ocul Surf*. 2007; 5: 75-92.
5. Bron AJ, de Paiva CS, Chauhan SK, et al. TFOS DEWS II pathophysiology report. *Ocul Surf*. 2017; 15: 438-510.

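### The sample size statement does not hold: 23 per group at an effect size of 0.85 gives about 80% power, not 90%, so the false-negative risk is about twice what is claimed

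*Combined protocol and SAP*

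**What the plan says.** All the inputs are in the Sample Size Calculation section of the combined protocol and SAP, except the allocation ratio.

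- Planning effect: "Assuming a large effect size of at least 0.85 for the PROKERA® Arm" against control, for the change in corneal staining score at 1 month.
- Sample size and power: "23 subjects per group or 46 subjects in total are needed to be randomized to yield an 90% power at a 2-tailed significance level".
- Test: "at a 2-tailed significance level of 0.05, using two-sample t-test".
- Interpretation of the effect, in the next sentence: "The effect size of 1.00 is equivalent to a reduction of approximately 35% in corneal fluorescein staining score from baseline".
- Dropout: "To further account for an around 10% dropout, the study plans to enroll and randomize 50 subjects in total".
- Allocation, under Study Subjects and Randomization: "Subjects will first be randomized in a 1:1 ratio to either PROKERA® Arm".

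The Statistical Methods section specifies a different primary analysis, an MMRM with the baseline staining score as covariate. The sample size is not based on it, and no correlation between baseline and follow-up is given.

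**The concern.** The effect size, the power and the number per group cannot all be right together. The section also uses two effect sizes: 0.85 in the calculation and 1.00 in the sentence that explains it in clinical terms. A reader cannot tell which effect the trial was designed to detect.

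The statement concerns the only primary effectiveness endpoint. If 90% is quoted beside a negative result, readers will take it as stronger evidence against an effect of 0.85 than the design can supply.

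**Working it through.** **Inputs.** From Sample Size Calculation: d = 0.85, two-sided alpha = 0.05, two-sample t-test, n = 23 per group. From Study Subjects and Randomization: 1:1 allocation.

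**Formula.** Power = P(|T| > t_crit), where T follows a noncentral t distribution with 2n − 2 degrees of freedom and noncentrality d × √(n/2).

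**1. The plan's own figure.**
- Degrees of freedom: 2 × 23 − 2 = 44, so t_crit = 2.015.
- Noncentrality: 0.85 × √(23/2) = 0.85 × 3.391 = 2.882.
- Power = 80.5%. The type II error is 19.5%, which is 1.95 times the implied 10%.
- Normal approximation: Φ(2.882 − 1.960) = Φ(0.922) = 82.2%.

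The stated 90% is not reproduced by either method, and the gap of 8 to 10 points is too large for rounding or choice of formula.

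**2. Sample size for 90% power at d = 0.85.**
- Normal approximation: 2 × (1.960 + 1.2816)² / 0.85² = 29.1, so 30 per group.
- t-test: the solved n is 30.08 (n = 30 gives 89.9%, n = 31 gives 90.9%), so 31 per group, or 62 evaluable.
- With 10% dropout: 62 / 0.9 = 68.9, which is 70 when rounded up to equal groups.

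**3. Where 23 per group could come from.**

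| Effect size | Power target | Solved n per group | Rounded up | Power at n = 23 |
|---|---|---|---|---|
| 0.85 | 80% | 22.73 | 23 | 80.5% |
| 1.00 | 90% | 22.02 | 23 | 91.2% |

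Both rows give exactly 23. The stated combination takes its effect size from the first row and its power from the second. With 23 per group, 90% power is reached only when d is about 0.98 or larger.

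**4. Effect of enrolling 50.**

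| Evaluable | Power at 0.85 | Power at 1.00 |
|---|---|---|
| 50 (25 + 25) | 83.8% | 93.4% |
| 46 (23 + 23) | 80.5% | 91.2% |
| 45 (22 + 23) | 79.6% | 90.6% |

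The dropout step is one subject short on its own terms: 50 × 0.9 = 45, below the 46 said to be needed, and 46 / 0.9 = 51.1, so 52 in equal groups.

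**5. Other ways to reach 90%.**
- A one-sided 0.05 test with 23 per group at d = 0.85 gives 88.4%, but the section specifies a two-tailed test.
- Baseline adjustment: if the covariate has correlation r with the outcome, the effective d is approximately 0.85 / √(1 − r²). Power is then 84% at r = 0.3, 87% at r = 0.4 and 90% at r = 0.5; the break-even value is about r = 0.49. These values of r are assumptions, since the document gives none.

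**The case against.** The strongest reply is that 0.85 may be the stray number. If the intended effect was 1.00, as the next sentence suggests, then 23 per group does give 90% power and the doubled false-negative risk disappears. The document cannot settle this. But 0.85 is the value stated for the calculation, and the 90% is attached to it. Because it is described as a minimum, it is the value at which the power has to hold.

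Two further arguments point to higher real power. The section cites an earlier study with an effect above 2.0, and power reaches 90% from about 0.98 upward. The planned MMRM adjusts for baseline and may be more efficient than the t-test. Both are fair limits: 80.5% describes the stated calculation at the stated minimum effect, not necessarily the planned analysis at the true effect. Neither rescues the 90%, because the document names the t-test as its basis and gives no correlation from which a gain could be credited.

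The dropout shortfall is minor. The rate is only approximate, 46 of 50 allows 8% loss, and Study Population/Duration makes 50 a minimum. Subjects who leave after the 1-month visit still contribute to the primary comparison, so 45 evaluable is a cautious case.

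**Conclusion.** The concern holds. On the plan's own inputs, power is 80.5% with 23 per group, and between 79.6% (45 evaluable) and 83.8% (all 50) at the planned enrolment. The stated 90% is wrong as written. The false-negative risk at d = 0.85 is about 20%, roughly double the 10% claimed.

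This rests on the unadjusted two-sided t-test that the section names and on a true effect equal to the stated minimum. It does not make the trial unsound, since 80% is a conventional power target. The section does have to be corrected, because it misstates the power for the primary endpoint and leaves the design effect ambiguous.

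**What to change.** Keep 50 subjects and rewrite the Sample Size Calculation so that effect size, power and number per group agree. Either version is consistent:

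- effect size 0.85, about 80% power, 23 per group; or
- effect size 1.00, about 90% power (91.2%), 23 per group. This version needs a reason for planning on 1.00, so that the assumption is not merely fitted to the sample size, and should also disclose the roughly 80% power at 0.85.

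Use the same effect size in the sentence on percentage reduction. The figure of about 35% belongs to 1.00. If 0.85 is kept, it must be restated; simple proportional scaling, which is an assumption, gives 0.85 × 35% = 29.75%, about 30%. Add the power that remains after 10% dropout: with 45 evaluable, about 80% at 0.85 or about 91% at 1.00.

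The cost is a short correction to one section, with no extra patients and no change to visits or analysis. The price is a less favourable stated figure. If the sponsor does want 90% at 0.85, the cost is instead 62 evaluable subjects, about 70 enrolled.
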